## **Surveys:**

### **Family Surveys:**

After enrollment into the research study, families will have a brief survey administered assessing their trust in medical providers (see appendix). In-person surveys will be given the option to take the survey on paper independently or administered by research staff verbally. Families for whom a translated survey is not available will have the survey administered using an interpreter. Families will receive two follow-up surveys (see appendix) assessing decisional regret and perceived benefits or harm of testing. The first follow-up survey will be administered within one week of the return of results (including the return of no results), and the second follow-up survey will be administered approximately one year after enrollment. If families are still in the hospital at the time of follow-up, research staff will attempt to meet the families bedside to conduct the survey. For families that are no longer in-patient at the time of follow-up, research staff will attempt to contact families by phone prior to administration of follow-up surveys and families will be offered the choice to decline further

surveys at that time. Barring a verbal decline for further surveys, families will have the choice to take the survey electronically e.g. via a REDCap survey or by phone. Families who chose the electronic survey will be told that if the survey is not completed within 72 hours, the research staff will contact them to conduct the survey by phone, with a possible second contact at a scheduled time.

### **Clinician Surveys:**

Within one week of the return of results (including the return of no results), clinicians caring for the patient will be asked to complete a brief survey (see appendix) regarding the clinical utility of genomic testing. The surveys may be administered in-person on paper or independently completed on paper or via email messaging to the providers' secured RCHSD or UCSD electronic mail account. Surveys will contain the minimum information required to identify the child in which the testing focuses on. It aims to identify what, if any, changes were made to the immediate management of the patient as a result of testing as well as general utility from the diagnosis. As these surveys are directed at obtaining clinical information about the patients and not assessing the clinicians as research subjects, the clinicians will not be enrolled as a part of this study. A second study of clinicians may be performed under a separate protocol in the future.

### **Data Sharing and Privacy:**

Samples that undergo clinical confirmation will be labeled as such and stored with identifiers for future confirmation and tracking. Following return of results, all other samples will have patient identifiers removed and be labeled with a research study ID and a second unique sample identifier. These unique identifiers will be linked with a Master List within the Rady Children's Institute for Genomic Research. The Master List will be password protected with access limited to research staff only. The Master List may take the form of an Excel file housed on an internal secure shared drive, with limited access, and/or a password protected, limited access REDCap database administered by RCH. Samples will also be tracked using the Rady Children's Clinical Genome Center's Laboratory Information Management System (LIMS) system.

Patient data will be stored securely in this HIPAA compliant sample tracking system separate from the electronic medical record. RCIGM is collaborating with researchers at UCSD; therefore data will be stored on the UCSD servers as well as the RCIGM servers. Researchers at UCSD will contribute expertise relevant to all aims of the study, especially to the ethical, social, and behavioral impacts and implications of newborn sequencing research. They will contribute expertise from previous studies of patient and physician response to genome sequencing for disease diagnosis, as well as attitudes and preferences about the personal genomic information for research. Researchers will analyze data collected from surveys of patients and physicians, draft manuscripts that report on findings from those data, and contribute to the design of future empirical studies focused on the ethical, social, and behavioral impacts of newborn genome sequencing.

### **Biorepositories:**

Sample testing, storage and analysis will adhere to the RCIGM Genomic Biorepository protocol, IRB# 160468. Following the clinical storage of samples in accordance with RCIGM CLIA laboratory requirements, all data and samples from participants in this study will be stored for future research. Coded and/or de-identified data will be shared with the RCIGM Genomic Biorepository (IRB# 160468).

Participants in this study will also be included in the Genomic Biorepository (IRB# 164068). Under this

protocol nucleic acids may be isolated and prepared for genomic sequencing with Standard Operating Procedures (SOP) at the Genomic Institute. Familial samples (for example, mother, father, affected or unaffected siblings) will also be obtained, and nucleic acids will also be sequenced per the Genomic Biorepository's SOP, as indicated, to assist in diagnosis of the acute medical condition in the infant. All sequencing and sample data will be stored by the Genomic Biorepository (IRB #160468). Clinical information will be shared with the Genomic Biorepository including referring clinician details, testing, symptoms, age of symptom onset and relevant medical and family history. All future research and data sharing will be regulated through the Genomic Biorepository protocol.

Similarly, this study will operate as a Newborn/Infant Biorepository. De-identified data collected from this study will be shared and aggregated with other sites participating in this or similar future research studies administered by the Rady Children's Institute for Genomic Research collecting genotypic and phenotypic data from infants. It is anticipated that a protocol mirroring this study will be made available as a multi-site research study hosted by Rady Children's Institute for Genomic Research subject to RCHSD/UCSD and Local IRB approval in the near future.

Data and sample sharing among researchers is key to enhancing the scientific community's understanding of genomics. De-identified data from this Newborn Biorepository will also be shared with public databases such as Clinvar and dbGAP as well as other research databases like the Longitudinal Pediatric Data Resource (LPDR) hosted by the Newborn Screening Translational Research Network (NBSTRN). Samples and data will be stored in the Rady Children's Institute for Genomic Research and Rady Children's Clinical Genome Center laboratory. The research team will review all cases to ensure that the phenotypic data and genotypic data being shared with other researchers as well as in publications and public databases are not individually identifiable. In rare cases where this information is determined to be identifiable, the research team will seek out specific permission from the family to release this information for the advancement of scientific understanding.

### **Optional Questions:**

Participants will also be offered the optional question to allow for the use of photographs as a part of this study. The RCH policy regarding the use of photography will be followed and the release form will be signed at the time photographs are taken. Photography may be used for publications. Whenever possible, the identifying features will be blocked. Names and other personal health identifiers will not be released as a part of publications. If, in the future, photographs are to be used for research purposes to test new technologies, including algorithms designed to identify phenotypic features, the PI will submit a separate protocol and obtain approval from the IRB for such research activity. Phenotypic features identified with this technology, as well as other phenotypic data collected from the medical record and patient assessments, may be shared with both public databases as well as in publications.

### **Opt-Out for Incidental Findings**

Families will be given the opportunity to opt-out of receiving actionable incidental results. In the event that our analysis incidentally finds a pathogenic variant for which a treatment or intervention exists to improve morbidity and/or mortality, families may choose to receive this additional information. We will not be intentionally looking for results unrelated to the primary cause of disease (secondary findings). All findings will be confirmed using an appropriate standard clinical testing method prior to the return of such results. Affected adult individuals will also be given the option to have their symptom-driven diagnosis reported clinically. All adults who are not patients at Rady Children's Hospital will be provided copies of their clinical results and advised to follow-up with their primary care provider. Results will be returned by, or on the instruction of, a

licensed clinical geneticist or genetic counsellor. These results will be discussed with both clinicians and the affected individual or their legal guardian following confirmation.

Unaffected subjects enrolled in this study will only receive results if they do not opt-out for incidental results. In the event that results are returned to unaffected participants who are not patients at Rady Children's Hospital, the participants will be provided with their results directly and advised to follow-up with their primary care provider. DNA from unaffected individuals and family members enrolled will be used primarily for comparison to the proband. Return of results will include inheritance patterns and risk for reoccurrence with Genetic Counsellors and/or Board Certified Clinical Geneticists available for families enrolled in this study.

## **Clinical Information Collection**

### **Patient clinical information**

We will collect patient identifiers (name, date of birth, family contact information, names, dates of birth, medical record numbers), demographic information (race, ethnicity, zip code at birth), birth information (birth history, APGAR score, interventions at birth, newborn screening results, pregnancy complications), clinical and phenotypic information (clinical symptoms, clinical presentations, lab values, imaging results, clinician notes, family histories and pedigrees), genetic testing information (types of tests ordered, test order and result dates, results of testing), and billing information (diagnostic codes, billing data, DRG data). After consent, information will be collected for this study at the following time points: at birth, at enrollment, at (or following) return of results, at time of significant clinical events and post significant clinical events (if any), at hospital discharge, at death if it occurs, at one year, and annually throughout the duration of this study. Additional data may be collected for long-term follow-up through the Genomic Biorepository to assess changes in the patient's medical condition and to possibly re-analyze sequences for symptom-driven diagnoses. This is often necessary to track disease progression, changes to clinical presentation and to correlate symptoms with genomic findings in light of new knowledge of genetic diseases.

### **Sequencing information**

All specific sequencing information will be kept in the Genome Biorepository per their protocol. We will collect quality metrics for each study run, run time length, total amount of data generated, and average coverage.

### **Data Analysis:**

Aggregate demographic and clinical information will be characterized and analyzed. Measures of outcomes and clinical utility will be determined for both arms of the study. Outcome measures will include Quality Adjusted Life Years saved, Disability Adjusted Life Years, mortality and severe morbidity. Clinical utility measures will include changes in medications, surgeries, diets, and other interventions, including institution of palliative care. Measures of diagnostic utility will also be collected (rate of diagnosis, type of diagnosis, time to diagnosis, completeness of diagnosis). Family perceptions of benefit and/or harm will be measured and results will be correlated to diagnoses and clinical reports of testing utility. Singleton versus family analysis diagnostic rates will be analyzed. Cost-effectiveness modelling will be developed. Utilization of genetic counseling and/or clinical genetics will be measured. The time spent consenting families will be measured as a baseline for future research.

This study will monitor parental feedback annually. In the event that a family states that this testing caused harm, additional information will be sought. Whenever possible, trends will be identified and changes to the research protocol will be submitted for IRB approval if harm can be mitigated. The study team will contact the

IRB in the event that 25% or more of the families enrolled perceived the testing to be harmful.

## **10. HUMAN SUBJECTS**

Up to 1000 acutely ill infants and their families will be randomized to receive rapid whole genome sequence versus rapid whole exome sequencing. We anticipate that we will enroll up to 2500 family members related to the 1000 acutely ill neonates and infants.

Multi-site enrollment:

- RCH will enroll ~1000 infants per year for an estimated total enrollment of ~250 to be enrolled and analyzed by the end of the NIH administrative supplement period ending September 2019.
  - Additional funding will be provided by Rady Children's Institute for Genomic Medicine.
- CMH will consult on Ethical, Legal and Social Implications of genomic testing in infants through their Pediatric Bioethics Center.
- Additional sites may be recruited to ensure enrollment goals are being met.

### **Sample size determination**

Preliminary results indicate that rapid trio WGS will result in a change in clinical utility index (CUI) ~50% of cases (a key secondary outcome). We propose that WES must yield a CUI of 40% or lower to justify the cost differential between WGS and WES. Using  $\alpha=0.05$ , we can achieve a power of 80% with 325 patient per arm, well below our proposed 500 patients per arm. Preliminary results indicate that rapid trio WGS is associated with 2.9 QALYs saved per infant tested (a key primary outcome). No similar analysis has been performed for WES. Additional patients, therefore, increase our power to assess differences in outcomes, and also compensates for technical or other issues that may cause some sample to be unanalyzable. Notably, we have proposed multiple measures of outcomes and clinical utility in addition to QALYs and CUI, respectively, and our power calculations do not correct for multiple testing. We feel this is acceptable for two reasons: First, these outcome variables are not completely independent making a Bonferroni correction overly conservative. Second, as there is little preexisting data on this subject, we felt a less conservative approach often utilized in preliminary studies is appropriate.

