## **5. LAY LANGUAGE SUMMARY OR SYNOPSIS (no more than one paragraph)**

This study will seek to determine if rapid genomic sequencing improves outcomes for acutely ill infants. We will enroll up to 1,000 acutely ill infants in a prospective, randomized, blinded study to either rapid Whole Genome Sequencing (WGS) or rapid Whole Exome Sequencing (WES, which is 2% of the genome and ~2-fold less expensive). Outcomes will be measured both by objective clinical measures and family perceptions (patient/family centered outcomes). Primary analysis of WGS or WES will be in infants alone. Secondary analysis, in infants who do not receive a diagnosis, will be of families – ideally trios (mother, father and affected infant), which is ~2-fold more expensive. Trios will be analyzed within the same randomization arm (WGS or WES). This study is designed to quantify which acutely ill infants benefit from rapid genomic sequencing, by how much they benefit, how they benefit, which rapid genomic sequencing method is superior, and the cost effectiveness of such testing.

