## **6. SPECIFIC AIMS**

**Specific Aim 1.** Determine if, and by how, much rapid WGS is associated with better outcomes than rapid WES in acutely ill infants. The null hypothesis is that both tests are equivalent. This may occur, for example, if the diagnosis rate is similar or the additional diagnoses from WGS do not alter clinical management.

**Specific Aim 2.** Determine if and by how much rapid WGS is associated with better perceived outcomes in parents of acutely ill infants than rapid WES in acutely ill infants. The null hypothesis is that both tests are

equivalent. In addition, this will be the first study to examine the family-centered outcomes of rapid genomic sequencing, and particularly in Hispanic/Latino families.

**Specific Aim 3.** To compare diagnostic rates, time to diagnosis, and outcomes of rapid genome-wide sequencing compared with historical matched cases who received standard care before genome-wide sequencing was available. The null hypothesis is that genome wide sequencing does not increase diagnosis rate, time to diagnosis or outcomes.

**Specific Aim 4.** To compare diagnostic rates of singleton analysis versus familial analysis (ideally trio) and the cost-effectiveness of each testing method (rapid singleton WGS, rapid singleton WES, rapid trio WGS and rapid trio WES). The null hypothesis is that adding familial sequencing data does not significantly increase diagnostic yield.

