Recently we implemented rapid (3 days) trio WGS at RCIGM. For 4 months we have enrolled acutely ill infants at RCHSD in the protocol “Genomic Biorepository: Protocol for the Collection, Storage, Analysis, and Distribution of Biological Samples, Genomic and Clinical Data (IRB #160468)”. Among 35 families with acutely infants nominated, 29 (83%) were enrolled. The fastest time to diagnosis was 41 hours from blood draw to communication of provisional diagnosis. On average, diagnosis occurred within one week. At time of submission, WGS had been interpreted in 29 families with 30 symptomatic infants, yielding informative data in 28. 15 (53%) of infants received diagnoses. In 14 (50%), the initial diagnosis was by rapid trio WGS. 13 patients had single nucleotide variants and two had structural variants. The leading mechanism of disease was de novo mutations causing dominant genetic disorders. Only two patients received diagnoses prior to completion of rapid trio WGS. Following diagnosis by rapid trio WGS, clinical management changed in 12 (43% of infants tested). Of these, medications were changed in 9 (32%) infants; One infant avoided needless major surgery; Palliative care was initiated in two infants with > \$6M potential healthcare savings. This data replicated our published previous experience at Children’s Mercy Hospital in Kansas City, but was remarkable since enrollment was much broader at RCHSD (namely, the 4 or 5 infants with greatest need of a definitive diagnosis each week).

Additionally, we recently concluded the first randomized, controlled, partially blinded, prospective trial of the 28-day diagnostic yield of rapid trio WGS plus conventional testing versus conventional testing in acutely ill NICU infants (the NIH-funded “NSIGHT” study). While the results are still being evaluated, we found that patients in the control arm of the study also received genetic diagnoses through next-generation sequencing, including WES and WGS, upon unblinding of neonatologists. Similarly, we observed a cross-over rate for compassionate use of WGS of 10%. Nevertheless, we found that the 28-day rate of diagnosis was 5 of 33 (15%) in the control arm and 14 of 32 in the rapid trio WGS arm (44%,  $p < 0.01$ ). Thus, provisionally, we conclude that rapid trio WGS has greater 28-day diagnostic yield than conventional testing. This study was not designed to evaluate clinical utility.

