The incidence of genetic diseases in acutely ill infants receiving NICU and PICU care is unknown since no large scale genomic sequencing study has been performed in this population. While genetic diseases are known to be a leading cause of death among infants, the impact of timely diagnosis in acutely ill infants on clinical care of these diseases is unknown. We propose a prospective, randomized study to compare outcomes in up to 1,000 acutely ill babies, all of whom will receive some form of genomic sequencing. We will use genomic

sequencing to prospectively test the hypothesis that rapid WGS confers significantly better outcomes to a subset of ill neonates/infants and their families than rapid WES or current clinical practice (clinical diagnosis and standard diagnostic tests). Molecular diagnostic yield, time to diagnosis and changes in management will be secondary outcomes.

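### The 325 infants per arm quoted for 80% power on CUI (50% v 40%, alpha 0.05) fits only an undeclared one-sided test; two-sided, 325 gives about 73% power and 80% needs 388 per arm.

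*Combined protocol and SAP*

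**What the plan says.** Sample size determination (section 10) takes a CUI of about 50% for rapid trio WGS, labels CUI a key secondary outcome, and sets the comparison value with the rule that "WES must yield a CUI of 40% or lower to justify the cost differential between WGS and WES". At alpha=0.05 it then says that "we can achieve a power of 80% with 325 patient per arm, well below our proposed 500 patients per arm". The paragraph gives no test, no sidedness and no continuity correction, and the Data Analysis text in section 9 names no test either. The surplus above 325 is meant to add power for other outcomes and to cover samples that cannot be analysed.

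Other sections bear on direction without settling it:

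- **Pointing one way (WGS better):** the Aim 1 objective, whether and by how much "rapid WGS is associated with better outcomes than rapid WES in acutely ill infants"; and the hypothesis in section 7, that "rapid WGS confers significantly better outcomes to a subset of ill neonates/infants and their families than rapid WES".
- **Not directional:** the Aim 1 null, "The null hypothesis is that both tests are equivalent. This may occur, for example, if the diagnosis rate is similar"; and the synopsis in section 5, which asks "which rapid genomic sequencing method is superior".

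The enrolment figure is an upper limit: "Up to 1000 acutely ill infants and their families will be randomized".

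**The concern.** An unqualified alpha=0.05 is normally read as two-sided, and a null of no difference together with a question about which method wins fits that reading. A two-sided 5% comparison of 50% with 40% needs clearly more than 325 per arm for 80% power.

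The number matters because it is the only power statement in the plan, and the only sample size the plan describes as enough. Since 500 per arm is a ceiling, anyone judging whether a recruitment shortfall is tolerable would measure it against 325. They could accept about 73% power believing it to be 80%. They would also overestimate how many unanalysable samples the design can absorb.

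**Working it through.** **Inputs.** p1 = 0.50 (WGS), p2 = 0.40 (WES, the upper bound of the plan's rule), alpha = 0.05, power 80%, stated n = 325 and proposed n = 500 per arm, all from Sample size determination. Allocation is 1:1 (section 9, Summary of design). The pooled rate is 0.45. Sidedness and continuity correction are not given, so each is tried both ways.

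**Sample size formula (pooled variance under the null).**

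n = [z_α·√(2·0.45·0.55) + z_β·√(0.25 + 0.24)]² / 0.10², with √(2·0.45·0.55) = 0.7036, √0.49 = 0.70 and z_β = 0.8416.

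With continuity correction: n_c = (n/4)·[1 + √(1 + 4/(n·0.10))]².

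**Step 1: reproduce 325.** One-sided 5%, z_α = 1.645:

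- n = (1.1573 + 0.5891)² / 0.01 = 305.0, so 305.
- n_c = 324.7, so **325**, an exact match.

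**Step 2: the two-sided reading.** z_α = 1.960:

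- n = (1.3790 + 0.5891)² / 0.01 = 387.3, so **388**.
- n_c = 407.1, so **408**.

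Two other two-sided formulas agree: unpooled variance gives 385 and arcsine 388. No two-sided variant tried comes within 3% of 325.

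**Step 3: power at a given n.**

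Power = Φ{[d·√n − z_α·0.7036] / 0.70}, with d = 0.10, or d = 0.10 − 1/n with continuity correction.

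At 325, two-sided:

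- Uncorrected: (1.8028 − 1.3790)/0.70 = 0.605, power 72.8%.
- Corrected: (1.7473 − 1.3790)/0.70 = 0.526, power 70.1%.

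| n per arm | One-sided 5% (corrected) | Two-sided 5% (corrected) |
|---|---|---|
| 325 | 82.2% (80.0%) | 72.8% (70.1%) |
| 500 | 93.8% (93.0%) | 89.0% (87.7%) |

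Exact enumeration at 325 per arm, two-sided, gives 73.7% for the chi-square test and 71.1% for both the Yates-corrected and Fisher tests. The result therefore does not depend on the normal approximation.

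**Step 4: the margin below 500.** On the plan's figure, 500 − 325 = 175 per arm. Two-sided, it is 500 − 388 = 112 uncorrected and 500 − 408 = 92 corrected.

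**Step 5: how far off in the planning inputs.**

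- For 325 per arm to give 80% power at 50% v 40%, two-sided alpha would have to be about 0.085 (0.10 corrected).
- At two-sided 0.05, 325 per arm has 80% power if the WES rate is 39.1% (38.8%). That is a difference of 10.9 (11.2) points instead of 10.

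**Step 6: after some loss of samples.** The plan gives no loss rate. Its one informative-data figure, from trio WGS only (section 7), is: "WGS had been interpreted in 29 families with 30 symptomatic infants, yielding informative data in 28". Assuming that rate held in both arms, 500 × 28/30 ≈ 467 per arm, with two-sided power of 86.8% (85.3%).

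**The case against.** The strongest reply is that 325 is a correct one-sided calculation, incompletely described. It matches one variant exactly, the cost rule works in one direction only, Aim 1 and the section 7 hypothesis favour WGS, and section 7 also states a belief that WGS is superior. A null of equality is compatible with a one-sided alternative, and the synopsis wording comes from a lay summary. On this view the 73% figure appears only when the reader supplies a two-sided test, which the plan does not declare either.

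Much of this stands. The figure is not an arithmetic slip, and a one-sided test may have been intended. But a directional hypothesis is not a declared one-sided test. The same paragraph explains why it makes no multiplicity correction and is silent on sidedness. A reader has no basis in the text for taking alpha=0.05 as anything but two-sided.

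The other points concern size, and they also stand. The gap equals about one percentage point in a WES rate given only as an upper bound. CUI is a secondary outcome. Both 388 and 408 lie below 500. It is also true that the lack of any power calculation for the QALY primary outcome is a larger gap in the same paragraph. These points limit the consequence; they do not make the stated figure valid on the conventional reading.

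**Conclusion.** The concern holds. The claim of 80% power with 325 per arm is true only for a one-sided 5% test, which the plan does not declare. Read two-sided, power at 325 is about 73% (70% corrected), the requirement is 388 (408) per arm, and the spare capacity is 112 (92) per arm instead of 175.

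This rests on the plan's own rates of 50% and 40%, equal allocation, and a two-sided reading of an unqualified alpha=0.05. The arithmetic is firm; what the authors intended is not known. The design itself is not endangered if the ceiling is reached, since two-sided power at 500 per arm is 89% (88%). It should be corrected because it is the plan's only power figure and the benchmark against which a shortfall would be judged.

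**What to change.** Restate the sentence in Sample size determination with the test named. For example: *For a CUI of 50% (WGS) v 40% (WES), a two-sided chi-square test at alpha=0.05 has 80% power with 388 infants per arm (408 with continuity correction); 500 per arm gives about 89% (88%).*

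If a one-sided test is intended, declare and justify it there, and give 305 per arm (325 with continuity correction).

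The cost is one sentence. The proposed 500 per arm stays as it is and no other section needs rewording. Under the two-sided option, the only loss is a smaller stated margin.

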## **4. ESTIMATED DURATION OF THE STUDY**

Enrollment in Rady Children's Hospital acute care settings to begin in 2017 and to continue through 2019, with follow-up including chart review of outcomes through 2025.

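### The 325 and 500 per arm in the sample-size section are not delivered by the plan's own ~250-infant estimate or by its pilot count, and no power or precision is given at that size

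*Combined protocol and SAP*

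**What the plan says.** **Size and power.** Section 10, Sample size determination, starts from the expectation that "rapid trio WGS will result in a change in clinical utility index (CUI) ~50% of cases". It requires a CUI of 40% or lower with WES to justify the extra cost of WGS. With alpha 0.05 it concludes: "we can achieve a power of 80% with 325 patient per arm, well below our proposed 500 patients per arm". It does not say whether the test is one- or two-sided, and it adds that "our power calculations do not correct for multiple testing". CUI is called a key secondary outcome.

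**Expected enrolment.** Earlier in section 10, up to 1,000 infants are to be randomised. The multi-site list then gives a rate of about 1,000 infants per year at the hospital "for an estimated total enrollment of ~250 to be enrolled and analyzed by the end of the NIH administrative supplement period ending September 2019". It says that further funding will be provided and that more sites may be recruited. No second enrolling site is named.

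**Window.** Section 4: "Enrollment in Rady Children's Hospital acute care settings to begin in 2017 and to continue through 2019".

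**Pilot.** Section 7, on 4 months at the same hospital: "Among 35 families with acutely infants nominated, 29 (83%) were enrolled". The same paragraph also describes enrolment as 4 or 5 infants each week.

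**Hypothesis.** Section 6, Aim 1: "The null hypothesis is that both tests are equivalent". The end of section 7 is directional: the study will "prospectively test the hypothesis that rapid WGS confers significantly better outcomes".

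**The concern.** The sample-size section reads as if 500 per arm were assured and 325 were a floor cleared with room to spare. Two other parts of the plan, the ~250 estimate and the pilot count, point to well under half of 325. The plan gives no power or precision at that size, although it expects those infants to be analysed.

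What is at stake is how a WGS v WES comparison on about 250 infants would be read. If a true 10-point gap in CUI would be missed more often than found, a non-significant result says little. Aim 1 frames the null as equivalence and WES is the cheaper test, so such a result could be taken as support for WES.

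**Working it through.** **Inputs.** CUI 50% (WGS) and 40% (WES), alpha 0.05, power 80%, 325 and 500 per arm: Sample size determination. 1:1 allocation: section 9, Summary of design. About 250 infants by September 2019: section 10. Enrolment 2017 through 2019: section 4, read as at most 36 months. 29 enrolled in 4 months, and 4 or 5 per week: section 7. Assumed: one infant per enrolled family and no loss.

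**1. Reproduce 325.** The uncorrected size per arm, with mean rate 0.45, is

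m = [z_a √(2 × 0.45 × 0.55) + z_b √(0.5 × 0.5 + 0.4 × 0.6)]² / 0.10².

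The continuity-corrected size is n = (m/4) × [1 + √(1 + 4/(0.10 m))]².

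| Test | Uncorrected | Corrected |
|---|---|---|
| One-sided 5% | 305 | **325** |
| Two-sided 5% | 388 | 408 |

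Of these four, only the one-sided test with continuity correction gives 325.

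**2. Accrual per arm.**
- Plan's estimate: 250 / 2 = 125.
- Pilot count: 29 / 4 = 7.25 per month; × 36 = 261 infants; / 2 ≈ 130.
- 4 or 5 enrolled per week: × 52 × 3 = 624 to 780 infants; / 2 = 312 to 390.
- If the two figures in the section 10 sentence were transposed, so that 250 is the yearly rate (an assumption): 250 × 33/12 ≈ 688 to 250 × 3 = 750 infants; / 2 ≈ 344 to 375.

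The first two fall far short of 325. The last two span it. None of the four reaches 500.

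**3. Power for 50% v 40%.** Uncorrected power = Φ{[0.10 √n − z_a √0.495] / √0.49}. At n = 125, two-sided: (1.118 − 1.379) / 0.70 = −0.373, so 35.5%. The corrected figures come from inverting the corrected formula in step 1. At n = 125 this gives m = 105.8, and one-sided (1.029 − 1.157) / 0.70 = −0.184, so 42.7%.

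| Per arm | Two-sided, uncorrected | Two-sided, corrected | One-sided, uncorrected | One-sided, corrected (basis of 325) |
|---|---|---|---|---|
| 125 | 35.5% | 30.8% | 47.8% | 42.7% |
| 130 | 36.7% | 32.1% | 49.0% | 44.1% |
| 325 | 72.8% | 70.1% | 82.2% | 80.0% |
| 500 | 89.0% | 87.7% | 93.8% | 93.0% |

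At 125-130 per arm every version is below 50%.

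**4. Precision.** 95% CI half-width = 1.96 √(0.49 / n): 12.3 points at 125 per arm, 7.6 at 325 and 6.1 at 500. At 125 per arm, starting from 50%, the difference detectable with 80% power (two-sided, uncorrected) is about 17 points.

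**The case against.** **About 250 is not a declared final size.** It is what is expected by the end of one funding period. Further funding is promised, sites may be added, a mirrored multi-site protocol is foreseen, section 4 is headed as an estimate, and 1,000 is a ceiling. This stands. A reader might infer that the trial as a whole has 35-40% power; the documents do not support that. They support only that this is roughly the two-sided power at the one enrolment total the plan forecasts.

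**The accrual text conflicts with itself.** A rate of about 1,000 per year would meet the target, and 4 or 5 enrolled per week, or a transposed 250 per year, could reach 325 per arm. This stands too, so the point cannot be separated from the clash inside the section 10 sentence. But 1,000 per year cannot be squared with about 250 in total from a 2017 start, and 4 or 5 per week does not match 29 enrolled from 35 nominated in 4 months. Even the two generous readings stop short of 500.

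**The pilot is not a forecast for this trial.** It ran under the biorepository protocol, and this study screens three intensive care censuses daily and takes nominations from other services. That is fair. Its weight comes from its agreement with the ~250 estimate.

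**Like must be compared with like.** The stated 80% belongs to 325 per arm, not to 500. A reader might set it against 36-37% and conclude that power is less than half of what is claimed. That mixes a one-sided corrected test with a two-sided uncorrected one; on the plan's own basis the comparison is 80% with 43-44%. Likewise, the size that carries the 80% is 325/125 = 2.6 times the expected one. A factor of four applies only to the proposed 500.

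**CUI is secondary and the plan calls its approach preliminary.** True, and this lowers the severity. It is nevertheless the only outcome with a power calculation.

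**Conclusion.** The point holds as an inconsistency between accrual and sample size. On the plan's ~250 estimate and its pilot count, neither 325 nor 500 per arm is reached by the end of 2019. At 125-130 per arm, power for 50% v 40% is about 36-37% two-sided without correction, or about 43-44% on the basis that reproduces 325. The interval at 125 per arm is about ±12 points around a gap of interest of 10. More generous accrual readings give about 310-390 per arm, so 325 is possible and 500 is not reached without more sites or more time.

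This assumes a window of at most 36 months, one infant per family, 1:1 allocation and no loss. Infants taken out of randomisation for ultra-rapid sequencing (section 9, Other Analysis) would lower the numbers further.

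The 325 itself is not an arithmetic error: it reproduces on one unstated convention. Nor do the documents plan a formal test at about 250 followed by continued enrolment, so this point gives no ground for dividing alpha. Severity: should-fix.

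**What to change.** In section 10:
- Reconcile the yearly rate and the total in the multi-site list with each other, with the window in section 4, with the two pilot descriptions in section 7, and with the 325 and 500 per arm.
- State the sidedness, and the continuity correction if one was used.
- Show power and CI width at about 125 per arm beside those at 325 and 500, all on the same basis.
- Present 500 per arm as conditional on added sites or a longer enrolment window.
- State that at about 250 infants WGS v WES will be reported as an estimate with its confidence interval, and that a non-significant difference is not evidence that the tests are equivalent.

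The cost is rewording only. No extra infants are needed for the change itself, and the stated power becomes less favourable.
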